Attachment 6: The VAS pain score

It is a straight line about 10 centimeters long. One end of the line is marked as "0", representing no pain, and the other end is marked as "10", representing the most severe pain imaginable. There are no other scale marks on the line, maintaining a simple visual presentation.

Self - assessment by the Patient: The patient marks a point on the line according to his or her current pain experience to represent the degree of pain. This process is completely completed by the patient independently to fully reflect his or her subjective pain experience. For example, if the patient feels mild pain, he or she may mark a point closer to the "0" end; if the pain is very severe, the mark will be closer to the "10" end.

Degree of Pain	VAS Score Range	Description
No Pain - Mild Pain	0 - 3 points	A score of 0 represents no pain at all; a score of 1 - 3 indicates mild pain, which has a relatively minor impact on daily life and generally does not require strong painkillers.
Moderate Pain	4 - 6 points	The pain begins to have a certain impact on daily life, intensifies during daily activities, and may require relief measures such as rest and the use of over-the-counter painkillers.
Severe Pain	7 - 10 points	Unbearable pain that has a severe impact on the quality of life, greatly interfering with daily activities, sleep, and emotions, and requires strong painkillers.

Attachment 7 Completeness of Specimens

Grading	Descriptions
Mesocolic plane	Smooth intact mesocolic excision.
Intramesocolic plane	The excision disrupts the mesocolon but do not reach down to the muscularis propria.
Muscularis propria plane	The excision disrupts the mesocolon and exposed the muscularis propria.

Protocol

A Multicenter Randomized Clinical Trial Comparing Surgical Site Infection after Intracorporeal Anastomosis and Extracorporeal Anastomosis for Left Colon Cancer (STARS)

Principal investigator:	[name]
Department:	Department of Gastrocolorectal Surgery
Version:	2.1
Release date:	July 16, 2023
[contact]
Email:	[contact]

Abstract

Title	A Multicenter Randomized Clinical Trial Comparing Surgical Site Infection after Total Laparoscopic and Laparoscopic-assisted Radical Surgery for Left Colon Cancer
Study Center	First Hospital of Jilin University Peking Union Medical College Hospital Cancer Hospital Affiliated to Fudan University Ruijin Hospital Affiliated to Shanghai Jiao Tong University School of Medicine Beijing Friendship Hospital, Capital Medical University PLA General Hospital Daping Hospital Affiliated to Army Military Medical University Shengjing Hospital Affiliated to China Medical University Chinese Academy of Medical Sciences Cancer Hospital China-Japan Union Hospital of Jilin University The First Affiliated Hospital of China Medical University Nanfang Hospital of Southern Medical University
Study Purpose	The purpose of this study is to investigate the effects of intracorporeal anastomosis and extracorporeal anastomosis in laparoscopic-assisted radical left hemicolectomy on surgical site infection. Also consider perioperative recovery, safety, and oncology outcomes.
Study Type	A prospective, multicenter, non-inferiority, two-arms, single-blind, randomized controlled study
Patients Selection	Inclusion Criteria: (1) age between 18 and 80 years; (2) histologically or cytologically confirmed left-sided colon cancer (distal transverse colon, left colic flexure, descending colon, or proximal sigmoid colon);

	
(3) clinical stage T1–4a, N0–2, and M0;
 
(4) Eastern Cooperative Oncology Group (ECOG) performance status ≤ 2;
 
(5) suitable for laparoscopic colectomy;
 
(6) no previous systemic chemotherapy or radiotherapy;
 
(7) willing to provide written informed consent and comply with the research procedures.

	
Exclusion criteria
 
(1) Have a history of malignant colorectal tumor or have been recently diagnosed with other malignant tumors.
 
(2) Patients with intestinal obstruction, intestinal perforation, intestinal bleeding, etc. who need emergency surgery.
 
(3) Patients who need to undergo combined organ resection or robot-assisted colectomy.
 
(4) Patients who are receiving preoperative neoadjuvant therapy.
 
(5) ASA grade $\geq IV$ and/or ECOG performance status score > 2.
 
(6) Patients with severe impairment of liver and kidney function, cardiopulmonary function, coagulation disorders or accompanied by severe underlying diseases and unable to tolerate surgery.
 
(7) Patients with a history of severe mental illness.
 
(8) Pregnant or lactating women.
 
(9) Patients who have a history of taking hormonal drugs.
 
(10) Diabetic patients whose blood sugar cannot be controlled to be within 6.1 - 8.3 mmol/L.
 
(11) Patients with other clinical and laboratory conditions that are considered by researchers as inappropriate for participating in this trial.

	
Exit criteria
 
(1) Patients with other non-tumor diseases that prevent them from

	
continuing to receive this treatment regimen.
 
(2) Patients who need emergency surgical resection due to intestinal obstruction, intestinal perforation, intestinal bleeding, etc. after being enrolled in the study.
 
(3) Patients with distant metastasis confirmed by intraoperative exploration or postoperative pathology, including liver, pelvic cavity, ovary, peritoneum, distant lymph node metastasis, etc.
 
(4) Patients who need combined organ resection as determined by intraoperative exploration.
 
(5) Patients who request to withdraw from this study cohort for various reasons after being enrolled in the study, or who cannot complete the study plan and follow-up for various reasons.

Intervention Methods	
Intracorporeal anastomosis group: Total laparoscopic technology is used. The tumor is resected according to surgical specifications for radical colon cancer surgery. Mesentery resection is performed under laparoscopy, and anastomosis is completed under laparoscopy. A small incision is made to extract the specimen.
 
Extracorporeal anastomosis group: Traditional laparoscopy-assisted technology is used. The tumor is resected according to surgical specifications for radical colon cancer surgery. A small incision is made in the middle of the abdomen to trim the mesentery, remove the specimen, and complete the anastomosis operation.

Primary Outcome Measures	The primary endpoint of this study was the surgical site infection within 30 days after surgery.
Follow-up Plan	The follow-up period for the primary endpoint was within 30 days after surgery. Follow-up is done through in-patient observation, outpatient consultations, and telephone inquiries. On the 30th day after surgery,

	
patients are required to return to the hospital for blood routine, liver function, kidney function, urinary routine, lung CT, and abdominal CT examinations. It also documents the patient's surgery-related complications and grades over this period, as well as solutions.
 
The total follow-up time for patients after surgery is 5 years. For patients with recurrent tumors, follow-up should continue for at least 3 years after recurrence or metastasis is discovered or until death.

Sample Size	350 cases
Statistical Methods	
1 Full analysis set
 
A comparative analysis of the primary outcomes will be conducted based on “modified intention-to-treat (mITT)”. In the mITT analysis, patients will be analyzed according to their randomization allocations.
 
2 Per-protocol analysis
 
In per-protocol analysis, only cases treated strictly in accordance with random groups and assigned treatment plans will be included. Patients who haven't been treated with a randomly assigned protocol will be excluded from the analysis.
 
3 As-treated analysis set
 
In the as-treated analysis set, we'll analyze patients according to the actual treatment plan they received instead of the allocated plan for random groups.

TABLE OF CONTENTS

1. Title.....	8
2. Introduction	8
3. Study Purpose and Endpoint.....	8
3.1 Study purpose	9
3.1.1 Main study purpose:	9
3.1.2 Secondary study purpose.....	9
3.2 Study endpoint.....	9

A Multicenter Randomized Clinical Trial Comparing Surgical Site Infection after Intracorporeal Anastomosis and Extracorporeal Anastomosis for Left Colon Cancer

2. Introduction

It is estimated that there were more than 1.09 million new cases of colon cancer and more than 500,000 deaths from colon cancer in 2018. In developed countries, the incidence of colon cancer is higher than in developing countries. Usually, cancers proximal to the splenic flexure are defined as right-sided and cancers at or distal to the splenic flexure are defined as left-sided (1). It is reported that left-sided colon cancer has different clinical and biological characteristics from right-sided colon cancer (2) and has a more favorable prognosis than the latter (3). Although neoadjuvant therapy and postoperative chemotherapy had been demonstrated to reduce the risk of tumor recurrence and death (4,5), surgery remains the main treatment for patients with potentially curable colon cancer(6). Currently, main surgical methods include traditional open surgery, minimally invasive surgery using laparoscopic techniques, and emerging robotic surgery. Compared with open surgery, laparoscopic surgery has achieved similar oncological outcomes in colon cancer or left-sided colon cancer (7,8). As for overall survival, laparoscopic surgery has been demonstrated oncologically safe, and was non-inferior to open surgery for patients with stage II or III colon cancer (9,10). However, surgical site infection (SSI) is one of the most common nosocomial infection in colonic surgery, with an incidence that varies between 5 and 30%(11,12). SSI is usually split into superficial incisional SSI, deep incisional SSI, and organ/space SSI(13,14). Data from the American College of Surgeons National Surgical Quality Improvement Program showed the overall SSI rate was 12.3%, and left resections had increased odds of superficial SSI compared with right resections (15). There is an urgent need to determine the incidence of SSI, as well as strategies to reduce SSI rate(16). The aim of STARS trial is to evaluate the incidence of SSI and safety of the intracorporeal anastomosis after left-sided colon surgery.

3. Study Purpose and Endpoint

3.1 Study purpose

3.1.1 Main study purpose:

To investigate the effects of intracorporeal anastomosis and extracorporeal anastomosis in laparoscopic-assisted radical left hemicolectomy on surgical site infection.

3.1.2 Secondary study purpose

To investigate the difference in postoperative recovery, safety, and oncology outcomes between intracorporeal anastomosis and extracorporeal anastomosis in laparoscopic-assisted radical left hemicolectomy.

3.2 Study endpoint

3.2.1 Primary endpoint and its definitions

The primary endpoint is SSI within 30 postoperative days. SSI was defined according to the U.S. Centers for Disease Control and Prevention (Attachment 1). The overall SSI included any superficial and deep incisional SSIs or organ/space SSI. Any patient suspected of having organ/space SSI underwent abdominal computed tomography (CT) or digestive contrast radiography to further confirm anastomotic leakage. In our study, anastomotic leakage was categorized as organ/space infection.

3.2.2 Secondary endpoint and its definitions

The secondary outcomes included:

(1) Operating time: It is defined as the period from cutting the skin to suturing the skin or doing enterostomy. It is measured in minutes.

(2) Total blood loss during operation: It is defined as the blood loss during operation and is measured in milliliters.

(3) Conversion to open surgery: It is defined as an abdominal incision larger than that necessary for specimen extraction.

(4) Postoperative complications: Postoperative complications are investigated within 30 days after an operation. It includes fever of unknown origin, bowel obstruction, anastomotic

leakage, SSI, other incisional complications, respiratory complications, urinary complications, cardiovascular and cerebrovascular complications, diarrhea, chylous fistula, intraperitoneal hemorrhage, digestive hemorrhage, gastroparesis, and others (including bacteremia, cholecystitis, ion discharge, pancreatitis, and mental and behavioral abnormalities). Complications are graded according to the Clavien–Dindo classification (17). The diagnosis of anastomotic leakage is based on the patient's postoperative clinical symptoms, signs of abdominal infection, or drainage properties and is confirmed by imaging (angiography or computed tomography) or secondary surgery. Postoperative intraperitoneal/digestive hemorrhage is defined as bloody drainage/bloody stool > 100 mL in 1 h or evidence of hemorrhage on CT, endoscopy, or angiography. The respiratory complications include pulmonary complications or pleural effusion. Urinary complications include infections, retention, and leakage.

(5) Completeness of specimens: It is evaluated according to the West classification.(18) The resected specimens will be classified into three groups according to the plane of dissection: mesocolic plane, intramesocolic plane, and muscularis propria plane

(6) Number of lymph nodes dissected: The number of lymph nodes in the mesentery will be calculated. Additionally, the metastatic lymph nodes will be counted. The pathological TNM staging was performed according to the American Joint Committee on Cancer (AJCC) Cancer Staging Manual, 8th edition.

(7) Postoperative recovery: Postoperative recovery information includes time to first flatus, time to first defecation, time to start food intake, and postoperative hospital stay. These are measured in days.

(8) Length of incision: The incision length is measured with an aseptic ruler at the end of the surgery, after the incision is sutured. It is measured in millimeters.

(9) Visual analog score (VAS) of pain: Pain severity was assessed 48 hours after the operation using a ruler about 10 cm long. The ruler is numbered from 0 to 10. 0–3 points indicate no to mild pain. 4–6 points represent moderate pain. 7–10 points stand for severe pain.

(10) 3-year disease-free survival (DFS) and 5-year overall survival (OS): DFS was defined as the time from randomization until the discovery of local recurrence, distant metastasis, or

death from the tumor. OS was defined as the time from randomization to death due to any cause.

4. Study design

[figure not shown]
4.1 Overall study design

This is a prospective, multicenter, non-inferiority, two-arms, single-blind, randomized controlled study.

4.2 Study time frame

The subject recruitment period is 3 years, and the follow-up period lasts 5 years. The entire study, which includes study establishment, patient recruitment, patient follow-up, and data analysis, is expected to take 8 years. We'll conduct a primary endpoint analysis of the study after all patients finish their first month of post-operative follow-up. Additionally, a second analysis of results involving survival data will be done after all patients complete 5 years of follow-up.

Figure 1 the study design flowchart

5. Study population

5.1 Inclusion criteria

- (1) age between 18 and 80 years;
- (2) histologically or cytologically confirmed left-sided colon cancer (distal transverse colon, left colic flexure, descending colon, or proximal sigmoid colon);
- (3) clinical stage T1–4a, N0–2, and M0;
- (4) Eastern Cooperative Oncology Group (ECOG) performance status ≤ 2 ;
- (5) suitable for laparoscopic colectomy;
- (6) no previous systemic chemotherapy or radiotherapy;

(7) willing to provide written informed consent and comply with the research procedures.

5.2 Exclusion criteria

- (1) Have a history of malignant colorectal tumor or have metastatic or multiple carcinoma.
- (2) Patients with intestinal obstruction, intestinal perforation, intestinal bleeding, etc. who need emergency surgery.
- (3) Patients who need to undergo combined organ resection or robot-assisted colectomy.
- (4) Patients who are receiving preoperative neoadjuvant therapy.
- (5) ASA grade \geq IV and/or ECOG performance status score > 2 .
- (6) Cardiopulmonary dysfunction (NYHA cardiac function classification II-IV), liver dysfunction (MELD score greater than 12), or kidney dysfunction (serum creatinine above the upper limit of normal);
- (7) Patients with severe psychiatric illness.
- (8) Pregnant or lactating women.
- (9) Patients who have a history of taking hormonal drugs.
- (10) Diabetic patients whose blood sugar cannot be controlled to be within 6.1 - 8.3 mmol/L.

(11) Patients with other clinical and laboratory conditions that are considered by researchers as inappropriate for participating in this trial.

5.3 Exit criteria

- (1) Patients with other non-tumor diseases that prevent them from continuing to receive this treatment regimen.
- (2) Patients who need emergency surgical resection due to intestinal obstruction, intestinal perforation, intestinal bleeding, etc. after being enrolled in the study.
- (3) Patients with distant metastasis confirmed by intraoperative exploration or postoperative pathology, including liver, pelvic cavity, ovary, peritoneum, distant lymph node metastasis, etc.
- (4) Patients who need combined organ resection as determined by intraoperative exploration.

(5) Patients who request to withdraw from this study cohort for various reasons after being enrolled in the study, or who cannot complete the study plan and follow-up for various reasons.

The data of patients who withdrew from the study were not used, and these patients were not allowed to re-enter the study.

6. Study treatment grouping

Experiment group: Total laparoscopic intracorporeal anastomosis group (IA group)

The tumor is resected according to surgical specifications for radical colon cancer surgery. Mesentery resection is performed under laparoscopy, and anastomosis is completed under laparoscopy. A small incision is made to extract the specimen after the anastomosis is completed.

Control group: Laparoscopy assisted extracorporeal anastomosis group (EA group)

The tumor is resected according to surgical specifications for radical colon cancer surgery. A small incision is made in the middle of the abdomen to trim the mesentery, remove the specimen, and complete the anastomosis. After completing the anastomosis, the incision will be sutured.

6.1 Randomization and allocation concealment

Randomization will be conducted immediately after recruitment. To guarantee randomization concealment adequately, and not be influenced either by the surgeon or the participants, randomization will be performed by a researcher who is not participating in this study from the Research Centre of Clinical Epidemiology (RCCE), Jilin University First Hospital. The random codes will be designed in a 1:1 ratio (experimental group or control group) using the R (version 3.3.3, University of Auckland, Auckland, New Zealand). The random codes will be sealed in an opaque envelope and handed to the researcher responsible for grouping in RCCE. The site investigators can submit the participants' details to the RCCE and apply for randomization through text messages, e-mail, or telephone application. The researcher responsible for grouping in RCCE will review patient eligibility. When grouping, the envelope with the unique identification number for the participant will be opened, and the group assignment will immediately be delivered to the researcher of the study site by RCCE through text messages, e-mail, or telephone.

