6.2 Blinding and unblinding

The clinical surgeons, outcome assessors, data recorders, and statisticians will all operate independently. Due to the nature of the surgical interventions, the surgeons will not be blinded to treatment allocation. However, the outcomes assessor who assess or analyze the end point will be blinded. The patients will also be blinded to group allocation to reduce the risk of bias. Unblinding will not be performed unless the finalization of the main data analysis or required for patient's safety. After the data analysis, we will have a blinded interpretation of the study results to minimize misleading data interpretation.

7. Intervention and study flow

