7.1 Preparation procedures

Prior to the surgical intervention, patients are required to undergo a series of preparation steps to ensure optimal conditions for surgery and to minimize the risk of complications. On the evening before the operation, patients will consume a solution containing polyethylene glycol electrolytes to cleanse the bowel. This bowel preparation is crucial for visualization during surgery and to reduce the risk of infection. The day before surgery, patients will also be administered oral antibiotics, specifically metronidazole at a dosage of 800 mg and gentamycin sulfate at 160 mg, to target a broad spectrum of potential infectious agents. Furthermore, as a prophylactic measure against infection, mezlocillin sodium will be given 20 minutes prior to the induction of anesthesia.

7.2 Surgical Techniques:

General Surgical Procedures: On the day of surgery, patients are positioned supine on the operating table with their legs spread to allow ample space for the surgical team. The surgeon and assistant will be positioned on the right side of the operating bed, facilitating access to the surgical site. The initial incision, approximately 10mm in size, will be made above the umbilicus using an open technique, which allows for the introduction of the primary port for laparoscopic instruments. Subsequently, four additional ports will be strategically placed under laparoscopic guidance. Throughout the procedure, the principles of complete mesocolic excision (CME) and central vascular ligation will be adhered to. This involves a medial-to-

lateral approach, where mesenteric vessels, including the inferior mesenteric vein, left colic artery, and one to two sigmoid arteries, are carefully exposed and divided at their origins using either absorbable or non-absorbable clips. The greater omentum is then separated from the transverse colon using a harmonic scalpel, and the splenic flexure and descending colon are mobilized.

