7.4 Patients compliance and exit

To improve patient compliance, before randomization, physicians will communicate with patients in detail about surgical procedures, possible random groupings, relevant and evolving treatment, and patient safety and security conditions. They will obtain informed consent to ensure patients clearly understand the treatment and research procedures. The randomization time should be as close as possible to the time before surgery (the day before surgery) to prevent accidental exclusion of patients after randomization. After randomization, patients can withdraw from the trial at any time. If a patient requests withdrawal from the study, the main researcher at their research center will communicate with them to avoid disrupting the balance of random groups due to exclusion. If the patient still insists on withdrawing, they will be removed from the trial. Clinical information relating to this patient will not be included in any data analysis related to this trial.

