4.5 Primary endpoint

The primary endpoint in this trial is surgical site infection (SSI) within 30 postoperative days. Cases that fail to complete the 30-day follow-up are treated as missing data. The SSI will be compared between groups in the mITT population, PP population, and AT population.

- Overall SSI, Categorical variable. The absolute risk differences and the corresponding 95% CI between two groups will be calculated. The 95% CI will be compared with the non-inferiority margin (5%).

The subtypes of SSI (Superficial or deep incisional SSI, and Organ/space SSI) will also be compared between the two groups. However, their 95% confidence interval will not be compared with the non-inferiority margin.

The independent risk factors for overall surgical site infection (SSI) will be analyzed in the AT population. In univariable analysis, continuous variables will be converted to categorical variables. Chi-square tests or Fisher's exact tests will be employed. The key variables are as follows.

- Sex (male, female);
- Age (≤ 65 years, > 65 years);
- Body Mass Index ($\leq 24 \text{kg/m}^2$, $> 24 \text{kg/m}^2$);
- American Society of Anesthesiologists grading (I, II, III);
- Eastern Cooperative Oncology Group performance status score (0, 1, 2);
- Tumor site (distal transverse colon, splenic flexure of colon, descending colon, and proximal sigmoid colon);
- NRS2002 score (≤ 2 points, > 2 points);
- Parenteral prophylactic antibiotics (Yes, No);
- Mechanical bowel preparation (No, only enema, only oral laxative, enema plus oral laxative);
- Oral antibiotic bowel preparation (Yes, No);
- Postoperative antibiotic use time (≥ 3 days, < 3 days);

- Pathological TNM stage (0, I, II, III);
- Overflow of intestinal contents during anastomosis (Yes, No);
- Operating time (≤ 180 mins, > 180 mins);
- Blood loss during operation (≤ 100 ml, > 100 ml);
- Blood transfusion during operation (Yes, No);
- Prophylactic enterostomy (Yes, No);
- Anastomosis methods (Side-to-side anastomosis, End-to-side anastomosis, End-to-end anastomosis)
- Intervention (intracorporeal anastomosis, extracorporeal anastomosis)

Factors clinically relevant to SSI after univariable analysis will be included in multivariable analysis. Logistic regression will be used in multivariable analysis to identify independent risk factors for SSI. The effect size will be estimated using odds ratios (ORs) with 95% confidence intervals.

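### The allocation is released before laparoscopic exploration, so exits decided in theatre, which leave the mITT population, are judged by a surgeon who can know the arm

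*Combined protocol and SAP*

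**What the plan says.** All references are to protocol v2.1 and SAP 1.0.

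- **Timing.** Section 6.1: "Randomization will be conducted immediately after recruitment". Section 7.4: "The randomization time should be as close as possible to the time before surgery (the day before surgery"), with the stated purpose of avoiding accidental exclusions after randomisation.
- **Release.** Under 6.1 the Research Centre of Clinical Epidemiology (RCCE) opens the envelope and "the group assignment will immediately be delivered to the researcher of the study site by RCCE", by text message, e-mail or telephone. Nothing withholds it until preparation or exploration is finished.
- **Blinding.** Section 6.2: "the surgeons will not be blinded to treatment allocation".
- **Exits.** Section 5.3, exit (4): "Patients who need combined organ resection as determined by intraoperative exploration". Exit (3) covers distant metastasis found at exploration or on postoperative pathology. Under 12.2.1 and SAP 4.2.1, patients who meet an exit criterion after randomisation are left out of the mITT population. SAP 4.3 makes the primary analysis unadjusted.
- **Preparation.** Section 7.1 sets one regimen for all patients: "On the evening before the operation, patients will consume a solution containing polyethylene glycol electrolytes to cleanse the bowel"; "The day before surgery, patients will also be administered oral antibiotics"; parenteral prophylaxis follows shortly before induction. SAP 4.5 nevertheless lists parenteral prophylaxis and oral antibiotics as yes/no, and mechanical preparation in four categories. SAP 4.4 lists all three, and postoperative antibiotic duration, among baseline characteristics.

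**The concern.** Whether a patient needs combined resection is a judgement, and under this plan it removes the patient from the primary population. If a surgeon who knows the arm makes that judgement even slightly differently for intracorporeal (IA) and extracorporeal (EA) patients, the two mITT groups are no longer comparable. No adjustment in the primary analysis would absorb the difference. Randomising on the day before surgery cannot prevent an exclusion that is decided on the operating table.

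The secondary issue is co-intervention. Some preparation against SSI also follows allocation, and the SAP presents it as baseline. A difference between arms would then look like chance imbalance at entry rather than a possible consequence of knowing the arm.

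**Working it through.** **Order of events**

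| Event | Under 6.1 | Under 7.4 |
|---|---|---|
| Oral antibiotics, day before | after allocation, if recruitment precedes that day | order not fixed |
| Bowel preparation, evening before | after, on the same condition | probably after |
| Parenteral prophylaxis | after | after |
| Exploration: exit (4), intraoperative part of exit (3) | after | after |
| Postoperative antibiotic duration | after | after |
| Exit (3) by pathology | after | after |

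The exits at exploration follow allocation on either reading. The preparation steps do so less uniformly.

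**The plan's own sample size.** Inputs (12.1, SAP 3): EA 13.3%, IA 8.0%, margin 5 points, one-sided 0.025, power 0.80, drop-out 20%. With unpooled variance,

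n = (1.960 + 0.842)² × (0.080 × 0.920 + 0.133 × 0.867) / (0.05 + 0.053)² = 7.849 × 0.1889 / 0.01061 = 139.8, so 140 per arm.

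140 / 0.80 = 175 per arm, 350 in total. This matches the plan, so the sample size is not in question.

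**Effect of a shift in the risk difference.** Assume IA is truly at the margin (18.3% v 13.3%) with 140 per arm.

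SE = √[(0.183 × 0.817 + 0.133 × 0.867) / 140] = 0.0435.

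False non-inferiority = Φ(−1.960 + shift / SE).

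- No shift: 2.5%.
- 1 point favouring IA: Φ(−1.730) = 4.2%.
- 2 points favouring IA: Φ(−1.500) = 6.7% (6.8% if the SE is recomputed at the shifted rate).

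**Effect of a shift the other way.** At the design rates (8.0% v 13.3%, 140 per arm), a shift against IA of 1 point lowers power from 0.80 to 0.70, and of 2 points to 0.58.

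**How exits could produce such a shift.** The documents give no exit rates, so these inputs are assumed: 175 per arm, true IA rate 18.3%, and five more exits in IA than in EA, with SSI risk 30% to 50%.

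- At 30%: (175 × 0.183 − 5 × 0.30) / 170 = 18.0%, a shift of 0.3 points; false non-inferiority 3.1%.
- At 50%: (175 × 0.183 − 5 × 0.50) / 170 = 17.4%, a shift of 0.9 points; false non-inferiority 4.3%.

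With 18 extra exits the same risks give shifts of 1.3 to 3.6 points and 5.3% to 15.7%. That is an extreme case.

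**The case against.** - **When the surgeon learns the arm is inferred.** Delivery is to the site researcher, and 6.2 says only that surgeons are not blinded. This stands as a limit: the surgeon can know the arm before exploration, but the documents do not say that the surgeon does.
- **Sections 6.1 and 7.4 may be compatible.** They agree if recruitment is completed the day before surgery. That is fair, and a clarification would settle the wording. It does not help with exits, because exploration follows allocation on both readings.
- **Preparation is standardised.** A reader might infer that the surgeon knows the arm before all preparation and antibiotics, and that the SAP expects preparation to differ by arm. The documents support neither. Section 7.1 requires one regimen without reference to arm, and the SAP fields may only record compliance. The order against same-day oral antibiotics is not fixed under 7.4. SAP 4.4 already tabulates these variables, and SAP 4.5 lists them beside the intervention as candidates for a supportive model in the as-treated population. What remains is that 7.1 and the SAP categories must be reconciled, and that variables set after allocation are not baseline.
- **The sizes are assumed.** This stands.
- **A later release has limits.** It does not reach exits on pathology, exit (5) or postoperative antibiotic duration. It needs central cover for twelve centres, and changing it mid-trial creates two allocation timings. All of this stands, but the exits judged at exploration would still be protected.

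**Conclusion.** The point holds as a cheap improvement. Exits (4) and the intraoperative part of (3) are decided after allocation by a surgeon who can know the arm, and they remove patients from the primary population. That can bias the unadjusted risk difference in either direction, and it defeats the stated aim of 7.4. The co-intervention issue is secondary: parenteral prophylaxis certainly follows allocation, and the evening bowel preparation probably does.

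It would be wrong to read this as evidence that exits or preparation did differ by arm; nothing in the documents shows that. A shift of 1 to 2 points favouring IA would raise false non-inferiority from 2.5% to about 4.2% to 6.7%, and the same shift against IA would cut power to 0.70 to 0.58. These figures show sensitivity and are not estimates.

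**What to change.** 1. Replace the timing sentences in 6.1 and 7.4 with one rule. Consent and eligibility review stay before surgery. RCCE releases the assignment by telephone, a route 6.1 already provides, only after laparoscopic exploration has shown that the existing intraoperative exit criteria (distant metastasis, combined resection) are not met. Add no new test of suitability for either anastomosis: it would be an undefined eligibility screen and could change the population.
2. For patients randomised under the current rule, report exits by arm and reason. Add a sensitivity analysis that keeps patients with intraoperative exits in their randomised arm where 30-day SSI is known. Section 5.3 says that data of withdrawn patients are not used, so state that this does not bar the analysis for exits decided by the surgeon.
3. In SAP 4.4, present postoperative antibiotic duration, and preparation given after allocation, by arm as post-allocation co-interventions. Reconcile 7.1 with the categories in SAP 4.4 and 4.5.

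Cost: a protocol amendment and a SAP revision, RCCE cover during operating lists, and a short wait in theatre. If recruitment has begun there will be two allocation timings, so record which applied to each patient. No extra patients or procedures are needed. Exits on postoperative pathology and exit (5) will still fall after allocation, which is why items 2 and 3 are needed as well.
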